9. TREATMENT

9.1. Product

9.1.1. Description

NMS-01940153E is a [REDACTED], potent small molecule inhibitor of MPS1 kinase, critical player in the control of mitosis.

NMS-01940153E is provided as 30 mg salt, [REDACTED]

[REDACTED] Each vial (primary packaging) is packaged in a labeled single small carton (secondary packaging). The labeling of packages complies with regulatory requirements of countries involved in the study as well as recommendations provided in Annex 13 of the European Guide to Good Manufacturing Practice.

9.1.2. Drug Preparation/Administration/Dispensing

NMS-01940153E will be administered only at the investigational site and for no reason will be delivered to the patient for administration outside the reference investigational site. The appropriate amount of NMS-01940153E to be administered will be calculated based on the body surface area (BSA) of each individual patient, calculated based on Mosteller formula:

$$\text{BSA (m}^2\text{)} = [\text{height (cm)} \times \text{weight (kg)} / 3600]^{1/2}$$

The 30 mg/vial powder for solution for infusion will be reconstituted with 10 mL of sterile water for injection; the freeze-dried cake will easily dissolve by manual shaking in not more than one minute. The obtained solution will be further diluted with 0.9% Sodium Chloride for

injection, according to the dose of NMS-01940153E to be administered. Details are reported in the Investigational Medicinal Product (IMP) module of the study manual.

Only qualified personnel familiar with procedures that minimize undue exposure to them and to the environment should undertake the preparation, handling, and safe disposal of chemotherapeutic agents.

9.1.3. Procedure for Handling Drug Spills

As NMS-01940153E is a cytotoxic agent, drug handling precautions as for cytotoxic agents should be followed. Avoid contact or inhalation. In case of skin contact, the affected area should be washed with soap and plenty of water. Any contaminated clothing should be removed. In case of eye-contact, rinse thoroughly with plenty of water. Seek medical advice as soon as possible. In case of accidental spill, caregivers should be instructed to wear protective (waterproof) gloves. Collect the spilled substance in a suitable container for disposal in accordance with the local regulations concerning handling and disposal of cytotoxic materials. Once the spilled drug has been collected, use a detergent and then wash thoroughly with plenty of water for removal.

9.1.4. Storage and Stability

The IMP must be stored in a locked room that can be accessed only by the Pharmacist, the Investigator, or another duly designated person, in the original packaging, at controlled room temperature (not above +25°C and 77°F) conditions.

On the basis of the available stability results, a shelf-life of 60 months at controlled room temperature not above +25°C and 77°F is assigned to the IMP.

The NMS-01940153E reconstituted/diluted solutions can be stored for not more than 4 hours at room temperature and ambient light conditions prior to patient administration. However, it is recommended to prepare the reconstituted/diluted solutions just before or close to the infusion time (further details are reported in the IMP module of the study manual).

9.1.5. Source of drug

NMS-01940153E will be manufactured, packaged and distributed by NerPharMa S.r.l., (Nerviano, Italy) in compliance with good manufacturing practice (GMP) guidelines and under Sponsor's direction. NMS-01940153E re-supplies may be obtained by contacting the Sponsor, according to instructions detailed in the IMP module of the study manual.

9.1.6. The study product

The study product must not be used outside the context of this protocol. Under no circumstances should the Investigator or site personnel supply study product to other Investigators or clinics, or allowed the supplies to be used other than as directed by this protocol without authorization from the Sponsor.

The study drug must be administered to patients, according to study schedule, until the criteria for withdrawal are met, as detailed in Section 10. Drug accountability should continue to be performed and documented until the patient's last dose of NMS-01940153E.

Adequate records on receipt, use, return, destruction or loss, or other disposition of medication must be maintained. Drug accountability will be provided by the investigational site by using either specific drug accountability forms provided by the Sponsor or records used by the pharmacy at the investigational site and agreed upfront with the Sponsor. In either case, information describing study drug supplies and their disposition, patient by patient, must be provided, signed by the Investigator (or the pharmacist or other person who dispensed the drug). Details are provided in the IMP module of the study manual.

After verification by the study monitor and upon authorization of the Sponsor, the unused drug vials may be destroyed at the site as dictated by the appropriate standard procedures of the participating institution and destruction must be documented; alternatively, all unused drug vials will be returned to the Manufacturer who will provide, on behalf of the Sponsor, to send them to destruction. All used drug vials should be discarded according to the standard institutional policy.

9.2. Treatment Administration

9.2.1. Treatment Dose and Schedule

NMS-01940153E will be administered IV for 3 consecutive weeks on days 1, 8, 15 followed by 1 week of rest, in a 28-day cycle. The total dose to be administered will be calculated based on patient's BSA (see Section 9.1.2). The duration of infusion will be dependent on the total dose to be administered:

- 1 hour infusion if ≤ 255 mg are administered
- 1 hour 30 minutes infusion if > 255 mg but < 375 mg are administered

The starting dose for the Phase I portion of the study is $100 \text{ mg/m}^2/\text{week}$, then according to the observed safety profile, dose increments of 25-35% will be applied until the MTD is reached. In presence of unacceptable toxicity observed at $100 \text{ mg/m}^2/\text{week}$, a lower dose level by 25-35% may be tested.

In the Phase II portion of the study, NMS-01940153E will be administered at the RP2D defined in the Phase I, as starting dose (see Section 5.2 for definitions).

9.2.2. Duration of Treatment

Patients may continue on study treatment until disease progression, unacceptable toxicity, withdrawal of consent by the patient or other discontinuation criteria are met (see Section 10). The study will be closed once that the last patient has left the study.

9.2.3. Dose Modifications

9.2.3.1. Dose Reductions/Treatment discontinuations

Dose reductions/treatment discontinuations may occur as a consequence of drug-related toxicities, during a cycle or at the start of a new cycle. All dose reductions/treatment discontinuations should be based on the most severe toxicity observed in the previous cycle and attributable to the study drug (according to the NCI CTCAE v 5.0). In the event of multiple toxicities, the dose reduction/treatment discontinuation should be based on the worst toxicity observed.

Any modification to the NMS-01940153E dose should be documented in the eCRF.

During treatment, doses can be de-escalated only twice, otherwise patients would have to be withdrawn.

Doses reduced for drug-related toxicity should generally not be re-escalated, even if there is minimal or no toxicity with the reduced dose according to [Table 6](#). However, intra-patient re-escalation back to the previous dose level may be permitted at the discretion of the Investigator after discussion with the Sponsor.

Recommended dose reductions or discontinuation criteria during the treatment cycle and at the start of the subsequent cycle are shown in [Table 6](#).

9.2.3.2. Re-treatment Criteria and Cycle Delay

A new cycle of treatment may begin when hematological and non-hematological toxicities are Grade ≤ 1 or have recovered to baseline values.

If these conditions are not met, treatment should be delayed for 1 week to allow for recovery. If, after 1-week delay, re-treatment criteria are met, then the new cycle can be initiated with a starting dose defined based on the toxicities observed in the previous cycle as outlined in the [Table 6](#).

If, after this period, toxicities do not recover to the pre-defined level, the patient will be withdrawn from the treatment, unless the Investigator believes treatment continuation is in the patient best interest. In this case, a maximum delay of 2 weeks (up to day 42 from cycle start) will be allowed.

Table 6. Dose Reductions/Treatment Discontinuations for NMS-01940153E Based on the Worst Grade (as per NCI CTCAE Criteria, Version 5.0) Observed During a Treatment Cycle and in the Prior Treatment Cycle

Toxicity	Dose Adjustment during treatment cycle	Next cycle Starting Dose
Hematological Toxicities		
Neutropenia Grade 3	Omit dose; when resolved to \leq Grade 1 within the same cycle, decrease one dose level.	Start at or maintain the decreased dose level.
Neutropenia Grade 4	Omit dose; when resolved to \leq Grade 1 within the same cycle, decrease one dose level.	Start at or maintain the decreased dose level.
Febrile Neutropenia	Omit dose; when resolved, decrease one dose level.	Start at or maintain the decreased dose level.
Thrombocytopenia Grade 3 associated with bleeding or thrombocytopenia Grade 4	Omit dose; when resolved to \leq Grade 2 within the same cycle, decrease one dose level.	Start at or maintain the decreased dose level.
Anemia Grade 3	Omit dose; when resolved to \leq Grade 2 within the same cycle, decrease one dose level.	Start at or maintain the decreased dose level.
Anemia Grade 4	Study treatment discontinuation.	Study treatment discontinuation.
Other Grade 3 Hematologic Toxicities	Omit dose; when resolved to \leq Grade 2 within the same cycle, decrease one dose level.	Start at or maintain the decreased dose level.
Other Grade 4 Hematologic Toxicities	Study treatment discontinuation.	Study treatment discontinuation.
Nausea and/or Vomiting		
Grade \geq 3 despite optimal management of the event §‡	Omit dose; when resolved to \leq Grade 2 within the same cycle, decrease one dose level.	Start at or maintain the decreased dose level.
Diarrhea		
Grade 2 despite optimal management of the event §	Omit dose; within the same cycle decrease one dose level.	Start at or maintain the decreased dose level.
Grade \geq 3 despite optimal management of the event §	Omit dose; when resolved to \leq Grade 2 within the same cycle, decrease one dose level.	Start at or maintain the decreased dose level.
Neurologic Toxicities (except insomnia/paraesthesia)		
Grade 2	Omit dose; when resolved to \leq Grade 1, decrease one dose level.	Start at or maintain the decreased dose level.
Grade $>$ 2	Consider discontinuation of study treatment based on risk/benefit assessment #.	Consider discontinuation of study treatment based on risk/benefit assessment #.
Other Non-Hematological Toxicities (except alopecia)		
Intolerable or persistent Grade 2 adverse events	Omit dose; when resolved to \leq Grade 2, maintain the dose level at first occurrence; at second occurrence, omit dose; when resolved to \leq Grade 2, decrease one dose level. .	At second occurrence, start at or maintain the decreased dose level.

Table 6. Dose Reductions/Treatment Discontinuations for NMS-01940153E Based on the Worst Grade (as per NCI CTCAE Criteria, Version 5.0) Observed During a Treatment Cycle and in the Prior Treatment Cycle

Toxicity	Dose Adjustment during treatment cycle	Next cycle Starting Dose
Grade 3	Omit dose; when resolved to \leq Grade 2, decrease one dose level.	Start at or maintain the decreased dose level.
Grade 4	Omit dose; when resolved to \leq Grade 2, decrease one dose level or consider study treatment discontinuation [#]	Start at or maintain the decreased dose level or consider study treatment discontinuation [#]
Grade \geq 3 hypersensitivity reaction suggestive of anaphylactic reaction [#]	Study treatment discontinuation	Study treatment discontinuation.

§ For prophylaxis and management of the events, see details in Supportive Care Sections 9.2.7.
 ‡ lasting longer than 48h without resolution to grade 2 or better and judged at least possibly related to NMS-01940153E.

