3.6. Safety results

Among 36 patients evaluable for first cycle Dose Limiting Toxicities, 3 DLTs were reported: grade 3 anemia, at 4 mg/m²/week; grade 4 hypertensive crisis, at 20 mg/m²/week; grade 3 fatigue, at 135 mg/m²/week [16].

The most frequent treatment emergent adverse events (TEAEs) reported in at least 15% of patients were fatigue (57.9%), anaemia (44.7%), nausea (31.6%), decreased appetite (28.9%), constipation, pain, vomiting (23.7% each), cough (21.1%), diarrhea (18.4%) and dyspnea (15.8%) [16].

The most frequent TEAEs related to NMS-01940153E reported in at least 10% of patients were anaemia (36.8%), fatigue (28.9%), nausea (21.1%), decreased appetite (15.8%), neutropenia (13.2%) and diarrhea (10.5%) [16].

Among the 4 patients treated at 67.5 mg/m²/week, the TEAE related to NMS-01940153E reported were nausea (2 patients G1), anemia (1 patient G2), decreased appetite (1 patient G1), fatigue (1 patient G1) and platelet count decreased (1 patient G3) [16].

Among the 7 patients treated at 135 mg/m²/week, the TEAE related to NMS-01940153E reported were anemia (1 patient G3, 3 patients G2), neutropenia (4 patients G3), decreased appetite (2 patients G2, 1 patient G1), diarrhoea (2 patients G2, 1 patient G1), fatigue (1 patient G3, 1 patient G2), nausea (1 patient G2, 1 patient G1), haemolysis (1 patient G1), keratitis (1 patient G3), mucosal inflammation (1 patient G3) and pain (1 patient G2) [16].

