5.2.1. Definition of DLTs

For this protocol, a DLT will be defined as any of the following events for which the relationship to NMS-01940153E cannot be definitely excluded. Toxicities are to be graded according to the NCI CTCAE version 5.0 [21].

Table 1. DLT criteria	
Hematological Toxicity	
Neutropenia	Grade 4 lasting >7 days or Grade 4 of any duration associated with Grade ≥ 2 infection
Febrile neutropenia	ANC <1000/mm ³ and a single temperature of >38.3 degrees C or a sustained temperature of ≥ 38 degrees C for more than one hour.
Thrombocytopenia	Grade 3 associated with any grade bleeding or Grade 4
Anaemia	Grade ≥ 4
Non-Hematological Toxicity	
Nausea, vomiting or diarrhea	Grade ≥ 3 despite optimal treatment
Signs of potential severe drug-induced liver injury as assessed according to Hy's law	Alanine aminotransferase (ALT) or aspartate aminotransferase (AST) >3 ULN and total bilirubin >2 ULN in the absence of cholestasis (alkaline phosphatase [ALP] <2 ULN) and no other reason can be identified.
Any other non-hematological toxicities;	Grade ≥ 3 toxicities unless clear alternate etiology is documented by the investigator and except: - asymptomatic Grade 3 electrolyte changes that can be successfully supplemented (e.g., hypokalemia) and resolve/recover to baseline within 72 hours - Grade 3 fatigue that improves to \leq Grade 2 in no more than 5 days - alopecia
Other significant toxicity	
Failure to complete the first cycle of treatment with at least 66% of the planned total dose due to toxicity possibly related to the study medication	-
Failure to start Cycle 2 for more than 1 week (day 36 or later) due to persistent Grade ≥ 2 toxicities possibly related to the study medication, excluding fatigue	-
Any toxicity that is possibly related to the study medication and requires the withdrawal of the patient from the study during the DLT observation period	-
Any on-study death not clearly due to the underlying disease or extraneous causes	-

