10. SUBJECT WITHDRAWAL FROM STUDY PARTICIPATION

Patients may withdraw from the study at any time at their own request, or they may be withdrawn at any time at the discretion of the Investigator or Sponsor for safety, behavioral, or administrative reasons.

If the patient does not return for a scheduled visit, every effort should be made to contact him/her. In any circumstance, every effort should be made to document patient outcome, if possible. The Investigator should inquire about the reason for withdrawal, request the patient to return for a final visit, if applicable, and follow-up with the patient regarding any unresolved adverse events.

If the patient withdraws consent for disclosure of future information, no further evaluations should be performed and no additional data should be collected. The Sponsor may retain and continue to use any data collected before such withdrawal of consent.

Patients may continue with therapy unless any of the following occurs:

- Disease progression by RECIST 1.1 at any time, unless there is reasonable evidence of clinical benefit to justify continuation on treatment, to be discussed with the Sponsor;
- Unacceptable drug-related toxicities incompatible with continuation of treatment with NMS-01940153E according to the judgment of the Investigator, even at a reduced dose;
- Any medical event requiring administration of an unauthorised concomitant treatment if it interferes with the study evaluations and/or if it jeopardises patient's safety (see Section 9.2.7);
- Change in the patient's medical status (including pregnancy) such that the Investigator believes that patient safety may be compromised or that it would be in the best patient's interest to stop treatment;
- Occurrence of permanent or significant incapacity or disability;
- Treatment delay for >1 week from day 28 of any cycle due to treatment related toxicity, unless the investigator believes treatment continuation is in the best patient's interest. In this case a maximum delay of 2 weeks is allowed;
- More than two dose de-escalations required;
- Substantial deviation from specified inclusion or exclusion criteria or non-compliance by the patient with protocol requirements;
- Patient's refusal to continue study treatment;
- Withdrawal of consent;

- Patient lost to follow up;
- Death;
- Study terminated by the Sponsor.

Patients will be withdrawn from the study in case of:

- Withdrawal of consent;
- Patient lost to follow up;
- Death;

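### The re-treatment rule in Protocol 9.2.3.2 does not exempt alopecia, so new alopecia above Grade 1 that lasts to day 42 ends treatment, although Table 6 asks for no dose action

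*Protocol*

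**What the plan says.** Protocol Section 9.2.3.2 opens with the start condition: "A new cycle of treatment may begin when hematological and non-hematological toxicities are Grade" 1 or lower, "or have recovered to baseline values". If the condition fails, the cycle is put back by 1 week. If after that week "toxicities do not recover to the pre-defined level, the patient will be withdrawn from the treatment". The exception is a patient whom the Investigator thinks should carry on, for whom "a maximum delay of 2 weeks (up to day 42 from cycle start) will be allowed".

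Section 10 lists as a reason to stop therapy "Treatment delay for >1 week from day 28 of any cycle due to treatment related toxicity", with the same 2-week ceiling. Sections 1.4 and 5.1 and footnote 19 of the Phase I and Phase II schedules repeat the limit for patients who cannot be retreated, whatever the cause. None of these texts exempts alopecia.

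Table 6 heads its residual group of rows "Other Non-Hematological Toxicities (except alopecia") and names alopecia nowhere else. Alopecia is also exempted in two other places: inclusion criterion 12, for after-effects of prior therapy, and the Grade 3 or higher non-hematological DLT item in Table 1 (repeated in SAP Section 9.8.2).

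**The concern.** The protocol sets alopecia aside at entry, in the Grade 3 or higher DLT item and in dose modification. The re-treatment sentence does not, and it decides whether the next cycle may start. Section 9.2.3.2 turns to Table 6 for the starting dose only once the re-treatment condition is met, so the exclusion in Table 6 does not carry back to the start condition.

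The rule applies at every cycle start in Phase II. A patient with persistent new alopecia above Grade 1 would lose the drug for an event on which the dose table takes no action. Otherwise the site would have to depart from the protocol as written.

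**Working it through.** **The rule applied to new-onset alopecia above Grade 1**

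1. Baseline is no alopecia, or a lower grade. The baseline clause therefore does not help while the alopecia persists.
2. Day 28: the Grade 1 condition fails, so the cycle is delayed.
3. Day 28 + 7 = day 35: if it is unresolved, the default is withdrawal from treatment.
4. Day 28 + 14 = day 42: this is the end of any delay the Investigator may allow. The condition still fails, and the text offers no further route to a new cycle.

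For alopecia present at entry and unchanged, step 1 differs: the patient is at baseline and the cycle may start.

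**Table 6 applied to the same event**

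- The hematological, nausea/vomiting, diarrhea and neurologic rows do not cover it.
- The residual non-hematological rows exclude it by name.
- Result: no omission, no reduction, no discontinuation.

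**How many patients could be affected**

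The documents give no alopecia rate, so only bounds can be derived. The inputs are from Protocol Section 3.6.

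- The list of related events seen in at least 10% of the 38 first-in-human patients does not include alopecia. Its lowest entry is diarrhea at 10.5%, and 4/38 = 10.5%. An event in 4 patients would therefore have been listed, so the ceiling for related alopecia of any grade is 3/38 = 7.9%.
- If that ceiling carries over to the planned limit of 40 Phase II patients: 40 × 3/38 = 3.2, or about 0 to 3 patients.
- Alopecia is absent from the related events listed at 67.5 mg/m²/week (4 patients) and 135 mg/m²/week (7 patients), the doses on either side of the RP2D of 100 mg/m²/week. That is 0/11, with an exact one-sided 95% upper limit of 1 − 0.05^(1/11) = 0.238, or 23.8%. Eleven patients are too few to exclude a rate above 7.9%.

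These bounds cover related alopecia of any grade. The rule affects only the cases that are new, above Grade 1 and unresolved at day 42.

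**The case against.** There are four arguments on the other side.

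1. *Investigator discretion.* The clause could be read as letting the Investigator resume dosing by day 42 without recovery, since what is capped is the delay. The text does not say this. The only thing it grants is a longer delay, and Section 10 grants the same. Even on the generous reading, a 1-week delay remains the default for an event that Table 6 leaves alone.
2. *Different jobs.* Table 6 sets dose and 9.2.3.2 sets timing, and the start condition is stricter elsewhere too: Grade 3 anemia may resume within a cycle at Grade 2, but a new cycle needs Grade 1 or baseline. This is true, and it means that the two texts are not in direct contradiction. It gives no reason to hold a cycle for alopecia, which the table excludes outright rather than setting a looser threshold.
3. *Other toxicities matter more.* New Grade 2 fatigue also blocks a cycle, and related fatigue occurred in 28.9% of first-in-human patients. That stands as a separate question. Fatigue is not excluded by name from Table 6, so the present argument does not extend to it.
4. *Rarity.* No case of alopecia appears in the safety results given, and sites would probably not withhold drug for it. Both points bear on size. They do not change what the rule says.

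**Conclusion.** The concern holds. Followed as written, Section 9.2.3.2 takes a patient off treatment for new alopecia above Grade 1 that persists to day 42, and no other text exempts alopecia from the re-treatment condition. The pattern of exemptions elsewhere suggests a drafting omission.

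The consequence is small. The figure of about 0 to 3 of 40 patients rests on carrying over a first-in-human ceiling that pools nine dose levels from 4 to 135 mg/m²/week. It counts any grade, so the affected subset is smaller and may be empty. No effect on ORR is claimed, and no analysis set or sample-size figure changes. This is an optional correction.

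**What to change.** In the first sentence of Protocol Section 9.2.3.2, insert the words (except alopecia) directly after the mention of hematological and non-hematological toxicities, and leave the rest of the sentence unchanged. Section 10 and the other statements of the delay limit can stay as they are, because alopecia would no longer cause a delay.

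The cost is two words in one sentence at the next amendment, with no extra data, no extra patients and no change to the SAP.

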5. TRIAL DESIGN AND DESIGN RATIONALE

This is a Phase I/II, open-label, non-randomized, multicenter study to explore safety, tolerability and antitumor activity of NMS-01940153E as single agent in adult patients with unresectable HCC previously treated with systemic therapy.

An independent Data Safety Monitoring Board (DSMB) will provide study oversight through periodic safety evaluations and make recommendations on study progress in the transition from Phase I to Phase II and at the planned interim analysis for the futility of Phase II.

The Phase I portion is designed as a dose-escalation study in sequential cohorts of patients aimed to obtain the MTD that is defined based on the DLTs observed in the first cycle of treatment. The selection of the starting dose and the dose escalation scheme is based on the safety information gained in the FIH study (EudraCT 2014-002023-10) and in consideration of the possible different tolerability in patients with compromised liver.

Once the MTD is identified and the safety profile of NMS-01940153E has been reviewed by the Investigators, the Sponsor and the independent DSMB and is considered adequate based on the entire Phase I data available, the Phase II portion of the study started.

The Phase II portion is designed as a two-stage study with an interim analysis for futility and stopping criteria for unacceptable toxicity to assess the antitumor activity of NMS-01940153E in adult patients with unresectable HCC previously treated with systemic therapy measured as objective response rate.

5.1. Treatment administration:

NMS-01940153E is supplied as labeled type I glass vials containing 30 mg/vial of powder for solution for infusion. Each labeled vial (primary packaging) is packaged in a labeled single small carton (secondary packaging).

Patients will receive treatment with NMS-01940153E administered as intravenous (IV) infusion for 3 consecutive weeks on days 1, 8, 15 followed by 1 week of rest, in a 28-day cycle. The duration of infusion will be dependent on the total dose to be administered:

- 1 hour infusion if ≤ 255 mg are administered
- 1 hour 30 minutes infusion if > 255 mg but < 375 mg are administered

Within one cycle, in case the patient cannot be retreated on the day foreseen because of toxicity, the dose will be skipped and the patient will be retreated at the next foreseen time-point.

Dose reduction/omission is foreseen based on toxicities observed (see Section [9.2.3.1](#)).

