5.3. Phase II

The Phase I part of the trial ended on May 30th, 2022 with the declaration of an RP2D of 100 mg/m²/week, and the study has already received a unanimous recommendation from an independent Data Safety Monitoring Board (DSMB) to continue the trial, moving to Phase II study.

The RP2D of 100 mg/m²/week, 3 of 4 weekly schedule, is justified based on safety, efficacy and pharmacokinetic considerations. The trend of dose-related neutropenia as the major safety feature points to the 100 mg/m²/week level as more tractable relative to 135 mg/m² (refer to full safety summaries in the IB). In terms of anti-tumor activity, the fact that, out of 6 evaluable, one confirmed RECIST partial response (despite one missed dose during the first two cycles) plus one highly prolonged stable disease were observed at 100 mg/m² as well as, out of 4 evaluable, 2 patients with substantial AFP reduction were observed points to reasonable activity at this dose level. Furthermore, pharmacokinetics at the 100 mg/m² dose level are in a meaningful range relative a continuous mouse tumor stabilization model predicting 0.2 uM average concentration threshold relative to the 100 mg/m² mean Cmax in HCC patients which is 7 fold higher at 1.35 uM and with AUC just slightly below the mouse threshold, 32.5 uM*h versus 35. Refer to IB for full PK descriptions. RECIST response and AFP reductions were observed at the 135 mg/m²/w level and PK was slightly higher but overall the anti-tumor pattern at 135 was similar to 100 mg/m². Therefore, overall, the 100 mg/m² level is justifiable as the RP2D.

In the Phase II portion, patients will receive the RP2D defined in the Phase I portion of the study as starting dose.

As soon as signs of toxicity are observed requiring a dose de-escalation, the dose will be decreased as described in Section 9.2.3.1, Table 6). A maximum of two dose decreases will be allowed, otherwise patient will have to be withdrawn from the study.

Patients will be enrolled in continuous, and continuously evaluated for endpoints, with a futility analysis and stopping criteria for unacceptable toxicity performed as described in Section 12. The enrollment will be stopped in the event of futility as described in Section 12, with no more than 20 subjects treated overall until non-futility can be declared, if appropriate. In any case, the Sponsor may stop or pause enrollments any time during the study based on safety, efficacy or strategic reasons.

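### Table 6 sets no working recovery grade before in-cycle re-dosing after an intolerable or persistent Grade 2 non-hematological event

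*Protocol*

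**What the plan says.** Protocol Section 5.3 makes Table 6 the working rule for Phase II: where toxicity requires de-escalation, "the dose will be decreased as described in Section 9.2.3.1, Table 6". Section 9.2.3.1 introduces the table as "Recommended dose reductions or discontinuation criteria during the treatment cycle and at the start of the subsequent cycle", so it has the status of a recommendation.

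The row at issue is triggered by "Intolerable or persistent Grade 2 adverse events". Its in-cycle instruction is to omit the dose and then, once the event is at Grade 2 or less, to "maintain the dose level at first occurrence; at second occurrence, omit dose". After that second omission the recovery grade is again 2 or less, and dosing resumes one level lower.

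Three other provisions bear on it:

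- **Section 5.1.** If toxicity prevents treatment on a planned day within a cycle, "the dose will be skipped and the patient will be retreated at the next foreseen time-point". No recovery grade is given.
- **Section 9.2.3.2.** "A new cycle of treatment may begin when hematological and non-hematological toxicities are Grade" 1 or less, or are back at baseline. This governs the start of a cycle, not a dose inside one.
- **Other Grade 2 rows of Table 6.** The neurologic row requires Grade 1 or less and then lowers the dose. The diarrhea row gives no recovery grade but also lowers the dose: "Omit dose; within the same cycle decrease one dose level".

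No footnote to Table 6 supplies a different in-cycle threshold for the row at issue. The SAP does not address dose modification rules.

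**The concern.** A recovery condition is useful only if the event that stops dosing fails it. Here the event is Grade 2 and the condition is Grade 2 or less, so the condition holds from the start. At first occurrence the row also keeps the dose level, so neither a better grade nor a lower dose stands between the omitted dose and the next one.

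Consider a patient whose day 8 dose was omitted for an intolerable Grade 2 event that is unchanged on day 15. One site may see the trigger still present and omit again. Another may see the recovery grade satisfied and give the full dose level. It is also unclear whether the unchanged event is still the first occurrence or now the second. That matters because the second leads to a dose reduction, and Sections 9.2.3.1 and 10 allow only two.

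The row is a catch-all, so it would cover events such as fatigue and decreased appetite. What is at stake is the safety of a dose given during unresolved toxicity, and uniform dosing across sites.

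**Working it through.** No sample size, power or error rate is involved, so there is no plan figure to reproduce. The check is logical: for each Table 6 row, is the trigger grade already among the grades at which dosing may resume?

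**Step 1. Count the rows.** Table 6 has 17 toxicity rows. Six give no numeric recovery grade: febrile neutropenia, Grade 4 anemia, other Grade 4 hematologic, Grade 2 diarrhea, neurologic above Grade 2, and Grade 3 or higher hypersensitivity. That leaves 17 − 6 = 11.

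**Step 2. Compare trigger and recovery grade in those 11.** Where a row covers several grades, the lowest is used.

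| Row | Trigger | Resume at | Dose on resuming |
|---|---|---|---|
| Neutropenia | 3 | ≤ 1 | lower |
| Neutropenia | 4 | ≤ 1 | lower |
| Thrombocytopenia (3 with bleeding, or 4) | 3 | ≤ 2 | lower |
| Anemia | 3 | ≤ 2 | lower |
| Other hematologic | 3 | ≤ 2 | lower |
| Nausea/vomiting | ≥ 3 | ≤ 2 | lower |
| Diarrhea | ≥ 3 | ≤ 2 | lower |
| Neurologic | 2 | ≤ 1 | lower |
| **Other non-hematological** | **2** | **≤ 2** | **same at first occurrence, lower at second** |
| Other non-hematological | 3 | ≤ 2 | lower |
| Other non-hematological | 4 | ≤ 2 | lower, or consider stopping |

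In 10 of the 11 the recovery grade is below the trigger. In the remaining row the trigger is 2 and the resume set is {0, 1, 2}, which contains the trigger. This is so at both occurrences.

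**Step 3. Look at what else protects the patient on resuming.** Eight rows resume at Grade 2 or less. Seven of them lower the dose. The eighth, at first occurrence, does not.

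**Step 4. Find which doses are exposed.** Doses fall on days 1, 8 and 15 of a 28-day cycle.

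- Day 1 of a later cycle is covered by the Grade 1 or baseline criterion.
- If day 8 is omitted, the next planned dose is day 15 of the same cycle, and only this row speaks to recovery.
- If day 15 is omitted, the next dose is day 1 of a new cycle, which is covered.

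So the exposed dose is day 15 after an omitted day 8: 1 of 3 doses in that cycle.

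**Step 5. Test the correction.** With Grade 1 or less the resume set is {0, 1}. It excludes the trigger grade, so the condition binds.

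**The case against.** The strongest reply is that the trigger is more than a grade. The event must be intolerable or persistent, so recovery can be read as the event no longer being either, at a severity of at most Grade 2. On that reading the condition works. Re-dosing at Grade 2 is also common in this table, and a lenient first step followed by a reduction is a coherent graduated scheme. This has some force: a careful investigator may well act that way. But the cell states its recovery condition only as a grade, Table 6 defines neither word, and the other rows that allow re-dosing at Grade 2 lower the dose.

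A reader might infer that the row contradicts itself and cancels its own omission. The documents do not support that. Section 5.1 makes the omitted dose a skipped one and moves treatment to the next planned day, so the omission takes effect whatever the recovery grade. What is missing is a recovery requirement before that next dose. Section 5.1 also leaves room to skip day 15 if toxicity prevents treatment then.

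The limits on harm stand in full. The table is a recommendation, Section 10 lets the investigator stop for unacceptable toxicity, and the next cycle has its own criterion.

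Finally, the text was machine-read, and a strict less-than sign misread as less-than-or-equal cannot be wholly excluded. The same symbol appears in both places in the cell, which makes this unlikely. If the source does have the strict sign, the row already means Grade 1 or less and needs no change.

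**Conclusion.** The row is wrong as written, and the error is minor. It gives no working recovery grade before the next in-cycle dose, and no other provision supplies one. The exposure is one dose, day 15 after an omitted day 8, in patients with an unresolved intolerable or persistent Grade 2 event of this class.

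The number of such patients cannot be estimated. Protocol Section 3.6 reports related Grade 2 decreased appetite in 2 of 7 first-in-human patients at 135 mg/m²/week, and fatigue and pain in 1 each. It does not say whether these were intolerable or persistent, and that is not the recommended Phase II dose of 100 mg/m²/week.

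A reader might go further and infer a threat to the response-rate result. Nothing in the documents supports that: the endpoint definition, the sample size and the error rates do not depend on this cell.

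The conclusion assumes that the printed symbol is correct and that sites apply the row by its stated grade.

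**What to change.** In both places in that cell, change the recovery condition from ≤ Grade 2 to **≤ Grade 1 or baseline**. This follows the neurologic Grade 2 row and the new-cycle criterion in Section 9.2.3.2. Leave the first- and second-occurrence steps as they are. It is one table cell in the next amendment.

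There are three costs:

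- A patient still at Grade 2 on day 15, and above baseline, misses that dose too. The cycle then delivers 1 of 3 planned doses (33%) rather than 2 of 3 (67%).
- The row becomes stricter on recovery grade than the Grade 3 and Grade 4 rows beneath it. Those rows resume at a reduced dose, whereas this one resumes at the same level at first occurrence, so the difference is defensible.
- The second-occurrence reduction would serve events that recur after recovery. An event that stays at Grade 2 above baseline throughout the cycle would not reach the reduced dose within that cycle.

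If the sponsor did intend re-dosing at a tolerable Grade 2, the lighter alternative is to keep the grade and add tolerability as an explicit condition. That avoids the extra missed dose, but it rests on a word the table does not define, so some variation between sites would remain.
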